-------------------------	--

	Finally, a secondary outcome of the research has to do with the effect mutations have on protein expression levels. We are aware that mutations change the distribution of proteins but to date we do not know whether the proteins of interest are actually expressed at lower levels, overly degraded or just shifted from a concentrated membrane localization to a more diffuse cytoplasmic distribution pattern. Western immunoblotting can help us answer this question and establish the actual mode of action of disease-causing mutations. Establishing the mechanism of disease is of pivotal importance both for diagnosis and for future mechanism-based therapies.
Sources of funding	British Heart Foundation/private donation
Anticipated start date:	02/01/2017
Anticipated primary completion date:	30/06/2026
Sponsor/Co-Sponsor	City St George's, University of London
Key Contact names	
Sponsor representative: [name] Email: [contact] [contact] [contact]
 
Chief Investigator: [name] Email: [contact]

Background

Analysis of myocardial samples has provided us with novel diagnostic markers for cardiomyopathies¹ and inflammatory heart disorders.² However, myocardial samples are difficult and risky to obtain from patients and impossible to obtain from family members, who do not manifest evidence of the disease but may still be carrying genetic alterations that put them at risk of SCD. We showed that the buccal mucosa expresses similar proteins to those expressed in the heart and may thus be used as a surrogate for the myocardium.³ We also showed that alterations in protein distribution occurring in the heart of patients with cardiomyopathies, also occur in their buccal cells, potentially providing us with a quick, easy, and totally risk-free means of diagnosis.³ We now want to apply this method to another group of heritable arrhythmic disorders; the cardiac channelopathies. In a sub-study we want to establish the mode of action of disease-causing mutations. By examining the actual expression levels (in addition to the distribution) of key proteins we can establish whether the mutations cause disease through reduced expression, increased protein degradation or merely protein re-distribution. Establishing the mechanism of disease pathogenesis will improve diagnosis, prognosis and form the basis for mechanism-based therapies.

Study Rationale

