Our preliminary studies suggest that we can use a buccal smear sample not only to identify those at risk of SCD but also to predict the genotype – which protein is bearing the disease-causing alteration. This correlation would allow us to significantly increase time-and cost-effectiveness of DNA sequencing by targeting analysis to those candidate proteins that appear to be mis-localized in the buccal mucosa. Timely identification of the disease-bearing protein is of pivotal importance as it allows for genotype-phenotype correlations; associations between a specific location/type of mutation and the course of the disease, thus improving risk stratification and patient management.

Another objective of this study could potentially be to evaluate the effect of treatment changes/interventions on protein distribution in the buccal mucosa, which we anticipate would mirror equivalent changes in the heart. For instance, the main electrical coupling protein in the heart (and the buccal mucosa) is Cx43. Patients with heart disease have been shown to have abnormal distribution of this protein at the cell-cell connections in both tissues. Remodelling of this protein has been previously associated with arrhythmias, and in certain cases it is considered a primary factor in their generation. If a patient is decided by his consultant cardiologist to start treatment with a new antiarrhythmic drug, it would be very informative to see whether distribution of Cx43 at the buccal mucosa is altered in response to the new treatment. This would allow us to make predictions in terms of risk stratification and treatment efficacy.

Finally, an objective of our sub-study, is to evaluate the mode of action of disease-causing mutations. We know that disease-causing mutations alter the distribution of key proteins. What we do not know is whether mutations affect the expression levels of key proteins. The approach we will use (Western immunoblotting) can show whether key proteins are expressed at normal or reduced levels. This will be of pivotal importance to establish the efficacy of mechanism-based therapies such as AAV.

Trial design

Overall design

Individuals will be recruited by their regular medical care providers. Once they have read the information sheet and understood the process entirely, if they agree to participate, they will sign

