Based on our pilot data from myocardial samples, mutations acting through haploinsufficiency lead to decreased protein expression levels as shown by western immunoblotting. We anticipate that we will be able to show this also in buccal cells from patients carrying such mutations. If, however, for unpredictable technical reasons we are unable to show changes in key protein expression levels using buccal samples after the first year, we shall stop recruiting participants for the sub-study.

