For the sub-study: tubes containing the buccal cells will be transferred to [name] laboratory. The tubes will be centrifuged and the cell pellet will be rinsed with PBS. The solution will be centrifuged again, PBS will be discarded and the sample will be resuspended in 10mM Tris-HCl with 1% SDS. Cell lysis will be achieved by sonication (15 pulses, 40% power output, 30% duty cycle). Sonicated samples will be centrifuged at 4 degrees for 20 minutes and the supernatant transferred to a new tube. Protein concentration will be measured using a BCA assay. 20 micrograms of protein solution will be mixed with laemelli buffer, boiled at 95 degrees for 5 minutes and loaded on a Tris gel. It will then be subjected to electrophoresis (150 volts, 40 minutes). Proteins separated on the gel will be transferred on a nitrocellulose membrane, which will be incubated with an antibody against the protein of interest. Membranes will then be incubated with a suitable secondary antibody, washed and exposed with the aid of chemiluminescent reagents. Images will be obtained via a Chemidoc 18 software to be kept in [name] notebook. All

samples will be de-identified. There shall be no way to link a tube containing a participant's cells with his identity. No sample will be used for any further study other than the one described in the information sheet. A study ID log containing participants name and unique study identification number will be kept separately from any other information related to the study in the ISF. Any samples and test results will only bear the unique participant ID number.

Safety Events

Definitions

Adverse Event (AE)—any untoward medical occurrence in a participant whether it is considered to be related to the intervention or not, that includes a clinical sign, symptom, or condition and /or an observation of a near incident. (This does not include pre-existing conditions recorded as such at baseline; continuous persistent disease or a symptom present at baseline that worsens following administration of trial intervention

Serious Adverse Event (SAE)—any Adverse Event or untoward medical occurrence in a trial participant that can be wholly or partly to the intervention which resulted in any of the following:

- Results in death; or
- Is life-threatening (places the participant, in the view of the Investigator, at immediate risk of death)

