Statistical design

Statistical input in trial design

Endpoints

Primary endpoints

The primary end point will be the presence of signal for a specific protein at the junctions of the buccal smear sample. No quantification of immunoreactive signal will be performed as this approach may increase bias. Accordingly, the results for each protein stain will be categorized as “present” or “absent”.

The end point of the sub-study will be whether a protein of interest is expressed at control levels or significantly decreased levels in the presence of a mutation. Accordingly, the results for each protein examined will be categorized as ‘control’ or ‘reduced’.

Secondary endpoints

Not applicable for this study.

Sample size and recruitment

Sample size calculation

The sample size was calculated based on the size of the St. George's and satellite centres' Arrhythmia Services. The number selected constitutes only a fraction of the individuals evaluated and regularly followed at the hospitals involved and will allow us to obtain statistically significant results for each arrhythmic disorder.

Planned recruitment rate

Based on the number of patients/family members evaluated at the arrhythmic services at City St George's, University of London, we estimate that we shall be recruiting approximately 200 individuals per year over the 4 year course of the study.

Statistical analysis plan

Summary of baseline data and flow of patients

The participants will include individuals from 3 groups:

1. Patients already diagnosed with an arrhythmic disorder
2. Relatives of patients diagnosed with arrhythmic disorders to establish risk status
3. Relatives of SCD victims for risk stratification.

There shall be no randomization of the participants and no differential treatment amongst the population. All individuals enrolled will only provide a buccal smear sample.

Primary endpoint analysis

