Regarding the secondary outcome of the analysis: patients with ACM bear mutations in genes encoding desmosomal proteins. These include desmoplakin, desmoglein2, desmocollin2, plakoglobin and plakophilin2 (PKP2). Buccal cells do not express PKP2. Instead they express a different isoform of the protein; plakophilin1 (PKP1). 15/15 ACM patients bearing mutations in PKP2 showed loss of PKP1 signal in their buccal mucosa. No patients bearing mutations in different genes showed this abnormality. Moreover, only patients bearing mutations in desmoplakin, desmoglein2 or desmocollin2 showed loss of desmoplakin signal in their buccal mucosa. Accordingly, using PKP1 distribution to predict the presence of mutations in PKP2 showed 100% specificity and sensitivity. This is a remarkable finding given how PKP1 and PKP2 are expressed by different genes localized on different chromosomes. And yet, a mutation in one

isoform expressed in one tissue affects distribution of a different isoform expressed in a different tissue. Similarly, using desmoplakin distribution to predict the presence of mutations in desmoplakin, desmoglein2 and desmocollin2 showed 100% specificity and sensitivity. We are now at a position to use the same approach in other, more common forms of arrhythmic disorders including the cardiac channelopathies.

We shall use the presence or absence of signal for specific proteins at buccal smears to:

1. predict clinical diagnosis for heritable arrhythmic disorders
2. predict the genes bearing disease-causing mutations
3. assess the effect of potential changes in treatment plan on the distribution of proteins (specifically Cx43)

We shall use the expression levels of specific proteins to establish

1. If mutations act through haploinsufficiency
2. If anti-arrhythmic medication corrects the distribution of connexin43 by increasing its production levels.

Sensitivity and other planned analyses (if applicable)

Please see explanation above

Interim analysis

If following the first year of the study, it appears that we are unable to predict "arrhythmic status" using such samples, we shall stop recruiting patients with cardiac channelopathies and will only focus on patients with cardiomyopathies, where the correlation is already proved

Committees involved in the trial

A trial management group (TMG) will be in place throughout the duration of the study

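### The sub-study's Western blot, read with the smear, can separate redistribution from loss of protein but not reduced synthesis from increased degradation, so the claim to establish mechanism should be narrowed

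*Combined protocol and SAP*

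**What the plan says.** The plan describes the sub-study's reach in several places, and not consistently.

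- **Background:** by looking at expression levels alongside distribution, "we can establish whether the mutations cause disease through reduced expression, increased protein degradation or merely protein re-distribution".
- **Study synopsis, secondary outcomes:** after naming the same three possibilities, "Western immunoblotting can help us answer this question and establish the actual mode of action of disease-causing mutations".
- **Secondary objectives:** a narrower statement, that the blot "can show whether key proteins are expressed at normal or reduced levels".
- **Primary endpoints (14.2.1):** the sub-study end point is "whether a protein of interest is expressed at control levels or significantly decreased levels in the presence of a mutation". Each result is one of two categories, control or reduced.
- **Secondary endpoint analysis:** expression levels will be used to establish "If mutations act through haploinsufficiency", and also whether anti-arrhythmic medication corrects connexin43 by raising its production.
- **Section 9.2 (stopping rules):** pilot myocardial data are cited as showing that "mutations acting through haploinsufficiency lead to decreased protein expression levels as shown by western immunoblotting".
- **DPIA, project description:** the expression levels will settle how selected mutations cause disease.

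The assay is set out under Laboratory procedures. Cells are lysed, "20 micrograms of protein solution will be mixed with laemelli buffer, boiled at 95 degrees for 5 minutes and loaded on a Tris gel", and the membrane is "incubated with an antibody against the protein of interest". Under Subsequent assessments, most sub-study participants give cells once and some may be asked for a second sample.

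**The concern.** A blot of this kind measures how much of the protein is in the cells when they are collected. That amount depends on both how fast the protein is made and how fast it is removed. A fall in the amount does not show which of the two changed, yet the Background lists them as separate mechanisms that the sub-study can tell apart.

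The Secondary endpoint analysis goes a step further and names haploinsufficiency as something the level will establish. Section 9.2 supports only the link from haploinsufficiency to a lower level. The conclusion needs the link in the other direction, and increased degradation, which the plan itself names, is a competing explanation.

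At stake is the mechanistic conclusion of the sub-study. Neither the smear endpoint nor the diagnostic aim depends on it.

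**Working it through.** The plan gives no sample size, power or error rate for the sub-study, so there is no figure to reproduce. The check is whether the planned measurements can identify the mechanism.

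**Inputs from the documents.** The blot result is control or reduced, and the smear result is signal present or absent at the junctions (Primary endpoints). The blot is of total lysate with an antibody to the target (Laboratory procedures). The data form in the DPIA records whether a disease-causing mutation is known. Its listed items do not include the type of variant. No section describes a measure of transcript, turnover or degradation products.

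**Assumptions.** At steady state, level = synthesis rate / degradation rate, with control set to 1 / 1 = 1. The rates below, the cut-offs for reduced (0.60, 0.75 and 0.90 of control) and the loss of junctional signal whenever protein is lost are illustrative. The documents give none of them.

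| Mechanism | Synthesis | Degradation | Level | Blot, at all three cut-offs | Smear |
|---|---|---|---|---|---|
| Control | 1 | 1 | 1.00 | control | present |
| Synthesis halved | 0.5 | 1 | 0.50 | reduced | absent |
| Degradation doubled | 1 | 2 | 0.50 | reduced | absent |
| Both changed | 0.75 | 1.5 | 0.50 | reduced | absent |
| Redistribution only | 1 | 1 | 1.00 | control | absent |

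**Reading the table.** Redistribution has its own pattern (control level, signal absent), so the blot and smear together separate it from the three rows in which protein is lost. Those three rows are identical on both measurements.

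**What a reduced result says about haploinsufficiency.** Let p be the probability, before the blot, that a mutation lowering the level does so through reduced synthesis rather than degradation. Let s be the probability of scoring reduced, taken as equal for both. Then

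P(reduced synthesis | reduced) = p·s / (p·s + (1 − p)·s) = p.

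The result leaves the probability where it was. If s differed between the mechanisms the blot would carry some information, but the plan gives no such values. More participants would not change this, and a second blot of the same kind has the same ambiguity.

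**Connexin43.** Suppose the level before treatment is 0.5 / 1 = 0.50. Doubling synthesis gives 1 / 1 = 1.00. Halving degradation gives 0.5 / 0.5 = 1.00. Both move the score from reduced to control, so the blot cannot attribute the change to production. If the level starts at control and the protein is only displaced, a rise above control has no category to fall into. The end point is also worded for the presence of a mutation, not for before and after treatment.

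**The case against.** The strongest reply is that the plan does not rely on the blot alone. The Background sentence opens by saying that levels are examined together with distribution, and the Informed consent section speaks of people who take part *also* in the sub-study, which suggests that a paired smear will exist. This stands. A reader might infer that a two-category endpoint cannot separate three mechanisms at all. The documents do not support that, because two binary readings give four combinations and redistribution can be told apart.

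A reader might also infer that every reduced result caused by degradation would be reported as haploinsufficiency, and put an error rate on it. No reporting rule says so: the recorded categories are control and reduced, and the synopsis says only that the blot can help. The documents give no share of mutations acting through degradation, so any error rate would merely repeat the share assumed.

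Third, section 9.2 expects to show the drop in carriers of mutations that act through haploinsufficiency, and the DPIA speaks of a few patients and selected mutations. In carriers already thought to have such a mutation, a reduced level is useful supporting evidence. This stands in part. No selection rule is written down, and where the mechanism is known from the selection, the blot confirms an expected consequence and does not establish the mechanism.

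Finally, the Secondary objectives already describe the assay correctly, and the remark there about mechanism-based therapies follows directly on the normal-or-reduced statement. That is so, and it is why the other sections can be brought into line with it.

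**Conclusion.** The point holds in a limited form. Of the three pairwise contrasts implied by the Background, the two involving redistribution can be addressed by reading blot and smear together. The third, reduced synthesis against increased degradation, cannot. The claims in the Background, the Secondary endpoint analysis and the DPIA that mechanism or haploinsufficiency will be established therefore exceed what the design can show. The connexin43 production claim has the same limit, together with the missing category for an increase.

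This rests on the assay as described, on level being the ratio of synthesis to degradation, and on a smear being available for each sub-study participant. The rates and cut-offs only illustrate the ambiguity. No count of affected conclusions can be given. The consequence is confined to the sub-study's mechanistic interpretation.

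**What to change.** 1. Reword the Background, the Secondary endpoint analysis and the DPIA project description to match the capability given in the Secondary objectives.
2. Report two findings: total level reduced; or total level not reduced with loss of junctional signal on the paired smear (redistribution). State that sub-study participants also provide a smear.
3. State that reduced synthesis and increased degradation are not distinguished, and describe a reduced level only as compatible with haploinsufficiency.
4. For connexin43, limit the conclusion to whether the total level changed, and add a category for an increase if that question is kept.
5. Optionally, add variant class (truncating or missense) to the data collection form to support a reading of haploinsufficiency. This is not needed to correct the overclaim.

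Items 1 to 3 are wording. Item 4 may add a scoring category. Item 5 needs a new field on a form that the care team already completes, and an update to the DPIA's data list. The price is a narrower mechanistic claim. No new assay or sample is needed, except that a smear would have to be taken from any sub-study participant who would not otherwise give one.
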